5.5 Treatment Compliance

To safely participate in a clinical study, all patients should complete pill diaries and planned laboratory studies. Unused drug will be returned to the study team who will contact the sponsor for instruction or follow local standard operating practices.

5.6 Discontinuation of Investigational Product

Subjects may be discontinued from protocol treatment in the following situations:

- Subject decision. The subject is at any time free to discontinue treatment, without prejudice to further treatment
- Adverse Event
- Severe non-compliance with the study protocol
- Bone marrow findings consistent with myelodysplastic syndrome (MDS)/acute myeloid leukemia (AML)
- Disease Progression (as defined by Section 7.6.7). In the absence of other indicators of disease progression, therapy should not be discontinued based on PSA rise alone.

5.6.1 Procedures for discontinuation of a subject from investigational product

A subject that discontinues will always be asked about the reason(s) for discontinuation and the presence of any adverse events. The Principal Investigator/Investigator will perform the best possible observation(s), test(s) and evaluation(s) as well as give appropriate medication and all possible measures for the safety of the subject. They should also immediately inform Sponsor of the withdrawal. Adverse events will be followed up for 30 days post last dose and all unused study drug should be returned by the subject.

If a subject is withdrawn from study, see Section 5.7.

5.6.2 Duration of follow-up

Patients will be followed for 30 days after removal from treatment or until death, whichever occurs first. Patients removed from treatment for unacceptable adverse events will be followed until resolution or stabilization of the adverse event.

All patients should be followed for MDS/AML and new primary malignancy assessment for up to 5 years after the patient completes the study per Section 7.7.1.

5.7 Patient Removal from Study

5.7.1 Screen failures

Screening failures are patients who do not fulfil the eligibility criteria for the study, and therefore will not be treated. Screen failures should be documented on the Screening and Enrollment Log. These patients will not have a study identification number assigned to them and will not receive study treatment.

5.7.2 Off study criteria

Patients can be taken off study at any time at their own request, or they may be withdrawn at the discretion of the investigator for safety, behavioral, administrative reasons or progression. The reason(s) for discontinuation from study will be documented and may include:

- Patient withdraws consent (termination of treatment and follow-up);
- Loss of ability to freely provide consent through imprisonment or involuntary incarceration for treatment;
- Patient is unable to comply with protocol requirements;
- Treating physician views continuation on the study would not be in the patient's best interest;
- Development of second malignancy (except for basal cell carcinoma or squamous cell carcinoma of the skin) that requires treatment, which would interfere with this study;
- Lost to Follow-up. If a research subject cannot be located to document survival after a period of 2 years, the subject may be considered "lost to follow-up." All attempts to contact the subject during the two years must be documented;

Termination of the study by The University of MichiganPatient completes protocol treatment and follow-up criteria

5.8 Patient Replacement

Patients who are enrolled in the study but do not start treatment with Olaparib, will be replaced and not included in analyses.

6. DRUG INFORMATION

6.1 Olaparib

Other names for the drug: AZD2281

Description: Olaparib is a potent PARP inhibitor (PARP-1, -2 and -3) that is being developed as an oral therapy, both as a monotherapy (including maintenance) and for combination with chemotherapy and other anti-cancer agents.

Mechanism of Action: Olaparib inhibits PARP enzymes (including PARP1, PARP2, and PARP3. PARP enzymes), which are involved in normal cellular homeostasis, such as DNA transcription, cell cycle regulation, and DNA repair.

Absorption: Following oral administration of olaparib tablets, absorption is rapid with peak plasma concentrations typically achieved between 1 to 3 hours after dosing. On multiple dosing there is no marked accumulation (accumulation ratio of 1.4 – 1.5 for twice daily dosing), with steady state exposures achieved within 3 to 4 days.

Limited data suggest that the systemic exposure (AUC) of olaparib increases less than proportionally with dose over the dose range of 100 to 400 mg, but the PK data were variable across trials.

Co-administration with a high fat meal slowed the rate (Tmax delayed by 2 hours) of absorption, but did not significantly alter the extent of olaparib absorption (mean AUC increased by approximately 20%)

Distribution: Olaparib had a mean (\pm standard deviation) apparent volume of distribution at steady state of 167 ± 196 L after a single 400 mg dose of olaparib. The *in vitro* protein binding of olaparib at plasma concentrations achieved following dosing at 400 mg twice daily is approximately 82%.

Metabolism: *In vitro*, CYP3A4 was shown to be the enzyme primarily responsible for the metabolism of olaparib.

Excretion: A mean (\pm standard deviation) terminal plasma half-life of 11.9 ± 4.8 hours and apparent plasma clearance of 8.6 ± 7.1 L/h were observed after a single 400 mg dose of olaparib.

Following a single dose of ^{14}C -olaparib, 86% of the dosed radioactivity was recovered within a 7-day collection period, 44% via the urine and 42% via the feces. The majority of the material was excreted as metabolites.

Based on preliminary data from a dedicated renal impairment trial, the mean AUC and Cmax of olaparib increased by 1.5 and 1.2-fold, respectively, when olaparib was dosed in patients with mild renal impairment ($\text{CLcr} = 50\text{-}80$ mL/min; N=14) compared to those with normal renal function ($\text{CLcr} > 80$ mL/min; N=8). There are no data in patients with $\text{CLcr} < 50$ mL/min or in patients on dialysis.

Side effects: The most common adverse reactions include GI distress (constipation, decreased appetite, diarrhea, indigestion, nausea, vomiting), dysgeusia, hematologic effects (anemia, leukopenia, neutropenia), headache, pneumonitis/cough/URI, arthralgias/myalgia and fatigue. Rare cases of myeloid leukemia have been observed also.

Drug Interactions: *In vitro*, olaparib was an inhibitor of CYP3A4 and an inducer of CYP2B6 at higher concentrations than are clinically achieved. Olaparib produced little/no inhibition of other CYP isozymes. *In vitro* studies have shown that olaparib is a substrate of CYP3A4.

Based on the data from a drug-interaction trial (N=57), the AUC and Cmax of olaparib increased by 2.7- and 1.4-fold, respectively, when olaparib was administered in combination with itraconazole, a strong CYP3A inhibitor. Simulations using physiologically-based pharmacokinetic (PBPK) models suggested that a moderate CYP3A inhibitor (fluconazole) may increase the AUC and Cmax of olaparib by 2- and 1.1-fold, respectively.

Based on the data from a drug-interaction trial (N=22), the AUC and Cmax of olaparib decreased by 87% and 71%, respectively, when olaparib was administered in combination with rifampicin, a strong CYP3A inducer. Simulations using PBPK models suggested that a moderate CYP3A inducer (efavirenz) may decrease the AUC and Cmax of olaparib by 50 - 60% and 20 - 30%, respectively. *In vitro* studies have shown that olaparib is a substrate of Pgp and an inhibitor of BCRP, OATP1B1, OCT1, OCT2, OAT3, MATE1 and MATE2K. The

clinical relevance of these findings is unknown. See Appendix B for further discussion.

Storage and stability: All study drugs should be kept in a secure place under appropriate storage conditions. The investigational product label on the bottle and the IB specifies the appropriate storage.

Preparation and Dispensing:

Olaparib tablets (100 mg or 150 mg tablets) will be packed in high-density polyethylene (HDPE) bottles with child-resistant closures. Each dosing container will contain 60 tablets and desiccant. Multiple bottles of study treatment may be required for dispensing in order to make up the desired dose. Bottles will be labeled per local regulations.

Administration:

Tablets are to be swallowed whole (not broken, chewed, crushed, dissolved or divided) with water. If given the same time as AZD6738, follow AZD6738 food instructions, otherwise olaparib may be taken with or without food.

If vomiting occurs shortly after the olaparib tablets are swallowed, the dose should only be replaced if all of the intact tablets can be seen and counted. Should any patient enrolled on the study miss a scheduled dose for whatever reason (e.g., as a result of forgetting to take the tablets or vomiting), the patient will be allowed to take the scheduled dose up to a maximum of 2 hours after that scheduled dose time. If greater than 2 hours after the scheduled dose time, the missed dose is not to be taken and the patient should take their allotted dose at the next scheduled time.

Availability: Supplied by the Astra-Zeneca Pharmaceutical Development R&D Supply Chain

Drug Accountability:

The investigator, or a responsible party designated by the investigator, must maintain a careful record of the inventory and disposition of the olaparib. The drug accountability records should capture drug receipt, drug dispensing, drug return and final disposition.

The investigators will be instructed by the Coordinating Center on the return or destruction of unused olaparib. If any olaparib is lost or damaged, its disposition should be documented in the source documents. Olaparib supplies will be retained at the clinical site pending instructions for disposition by the Coordinating Center.

6.2 **AZD6738**

Description: AZD6738 is a potent ATR inhibitor that is being developed as an oral therapy, both as a monotherapy and in combination with chemotherapy and other anti-cancer agents.

Mechanism of Action: AZD6738 inhibits ATR, which is involved in cell cycle checkpoint regulation, stalled replication fork resolution, single strand break repair (with Replication Protein A) and double strand break repair (with ATR Interacting Protein).

Distribution: AZD6738 has an estimated volume of distribution by modeling of 1 L/kg. The *in vitro* protein binding of AZD6738 at plasma concentrations achieved following planned dosing is approximately 87%.

Metabolism: *In vitro*, CYP3A4 was shown to be the enzyme primarily responsible for the metabolism of AZD6738.

Side effects: The most common adverse events are thrombocytopenia, anemia, neutropenia, nausea, vomiting and fatigue.

Drug Interactions: AZD6738 is metabolized by CYP3A4 and potentially inhibits organic anion transporting polypeptide 1B1 (OATP1B1) and P-glycoprotein (Pgp). At clinically relevant doses, it is unlikely to induce CYP1A2, CYP2B6 or CYP3A4. See Appendix B for discussion of management of potential drug interactions.

Storage and stability: All study drugs should be kept in a secure place under appropriate storage conditions. The investigational product label on the bottle and the IB specifies the appropriate storage.

Preparation and Dispensing:

AZD6738 will be supplied as tablets containing 20 mg, or 80 mg of drug. AZD6738 tablets will be packed in HDPE bottles with child-resistant closures. Bottles will be labeled per local regulations.

Administration:

AZD6738 tablets are to be swallowed whole (not broken, chewed, crushed, dissolved or divided) with water at the same time as the morning dose of olaparib and with fasting 2 hours prior to dosing and 1 afterwards.

If vomiting occurs shortly after the AZD6738 tablets are swallowed, the dose should only be replaced if all of the intact tablets can be seen and counted. Should any patient enrolled on the study miss a scheduled dose for whatever reason (e.g., as a result of forgetting to take the tablets or vomiting), the patient will be allowed to take the scheduled dose up to a maximum of 2 hours after that scheduled dose time. If greater than 2 hours after the scheduled dose time, the missed dose is not to be taken and the patient should take their allotted dose at the next scheduled time.

Availability: Supplied by the Astra-Zeneca Pharmaceutical Development R&D Supply Chain.

Drug Accountability:

The investigator, or a responsible party designated by the investigator, must maintain a careful record of the inventory and disposition of AZD6738. The drug accountability records should capture drug receipt, drug dispensing, drug return and final disposition.

The investigators will be instructed by the Coordinating Center on the return or destruction of unused AZD6738. If any AZD6738 is lost or damaged, its disposition should be documented in

the source documents. AZD6738 supplies will be retained at the clinical site pending instructions for disposition by the Coordinating Center.

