4.3.2 Concomitant treatments

AZD6738 is an investigational drug for which no data on *in vivo* interactions are currently available. Potential interaction is considered on the basis of preclinical *in vitro* data only.

The lists of CYP and transporter inhibitors/inducers, and CYP and transporter substrates are available in **Appendix B**. They are not exhaustive and the absence of a drug from these lists does not imply that its combination with AZD6738 is safe. If AZD6738 is being administered in combination, potential interactions of the combination partner should also be considered. **Olaparib** also has concomitant interactions and may require dose reduction if a strong or moderate CYP3A is required for a short period while on study.

- The principal enzyme for metabolizing AZD6738 is CYP3A, olaparib is also metabolized similarly. Subjects should avoid concomitant drugs, herbal supplements and/or ingestion of foods known to modulate CYP3A activity from the time they enter the screening period until 28 days after the last dose of study treatment.
- Prior to study medication, use of potent inducers or inhibitors of CYP3A are not permitted. For subjects taking any of these drugs (examples provided in **Appendix B**) the required wash-out periods before starting AZD6738 is described.
- While on study medication, if there is no suitable alternative concomitant medication other than a potent inhibitor of CYP3A, the investigator **must** interrupt AZD6738 for the duration of the potent CYP3A inhibitor and wait for the required wash-out period (five half-lives) before dosing AZD6738 again. If potent CYP3A inducers are considered necessary for the patient's safety and welfare, this may diminish the clinical efficacy of AZD6738 and the patient should be monitored carefully for any change in the efficacy of study treatment. Olaparib may also require adjustment. Refer to **Appendix B** for additional guidance.
- AZD6738 is a Pgp substrate. Co-administration of Pgp inhibitors or inducers may affect exposure to AZD6738 and, therefore, should be minimized if possible. Refer to **Appendix B** for additional guidance.

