Appendix B Guidelines Regarding Potential Interactions with Concomitant Medications

AZD6738 is an investigational drug for which no data on *in vivo* interactions are currently available. Potential interaction is considered on the basis of preclinical *in vitro* data only. The lists of CYP and transporter inhibitors/inducers, and CYP and transporter substrates are available in this appendix. They are not exhaustive and the absence of a drug from these lists does not imply that its combination with AZD6738 is safe. If AZD6738 is being administered in combination, potential interactions of the combination partner should also be considered.

Restrictions regarding drugs affecting CYP3A metabolism

There are currently no data confirming that there is a pharmacokinetic (PK) interaction between these agents and AZD6738; a potential interaction is considered on the basis of preclinical and *in vitro* data only. AZD6738 is predominantly eliminated via CYP3A metabolism (approximately 60%), therefore CYP3A inhibitors or inducers may increase or decrease exposure to AZD6738, respectively. Potent inhibitors or inducers of CYP3A should not be combined with AZD6738.

These lists are not intended to be exhaustive, and similar restrictions will apply to other agents that are known to modulate CYP3A activity. Please contact AstraZeneca with any queries you have on this issue. Please refer to full prescribing information for all drugs prior to co-administration with AZD6738.

**TABLE 8: Drugs Known to be Inhibitors and inducers of CYP3A
- manage by stopping/not using these medications**

Potent CYP3A inhibitors		Potent CYP3A inducers
boceprevir	nefazodone	avasimibe
clarithromycin	nelfinavir	carbamazepine
conivaptan	posaconazole	enzalutamide
elvitegravir/ ritonavir	ritonavir	mitotane
fluconazole	saquinavir	phenobarbital
grapefruit juice^a	telaprevir	phenytoin
indinavir	telithromycin	rifabutin
itraconazole	tipranavir/RIT	rifampin
ketoconazole	troleanomycin	St John's Wort
lopinavir/ RIT	voriconazole	
mibefradil		

List created using the University of Washington Drug-Drug Interaction Database January 2013.
RIT = Ritonavir.
Ritonavir has dual effects of simultaneous CYP3A inhibition and induction, and the net pharmacokinetic outcome during chronic ritonavir therapy is inhibition of CYP3A activity
a. Double-strength grapefruit juice

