**Table 14: Drugs known to be substrates of BCRP
- may co-administer, be aware of potential drug toxicity**

Anthracyclines	Mitoxantrone
Daunorubicin	nucleoside analogs
Doxorubicin	prazosin
Topotecan	pantoprazole
SN-38	topotecan
Irinotecan	rosuvastatin and other statins
Methotrexate	teriflunomide
Imatinib	chlorothiazide
Irinotecan	

List created using <https://www.solvobiotech.com/transporters/bcrp>

Olaparib:

This is guidance on management of olaparib on study when a strong or moderate CYP3A must be used for a short time.

If a strong CYP3A inhibitor must be used, olaparib should be dose reduced to 100 mg daily for the duration of concomitant therapy and for 5 half-lives afterwards. If a moderate CYP3A inhibitor must be used, olaparib should be reduced to 150 mg po twice a day for the duration of concomitant therapy with the moderate inhibitor and for 3 half-lives afterwards. After washout, olaparib may be increased to full prior dose.

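### Fluconazole is a moderate CYP3A inhibitor in Section 6.1 but listed as potent in Appendix B Table 8, so a site that takes the class from Table 8 could give olaparib 100 mg daily instead of 150 mg twice a day.

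*Combined protocol and SAP*

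**What the plan says.** Section 6.1, Drug Interactions, classes two inhibitors for olaparib. Itraconazole is strong: AUC rose 2.7-fold "when olaparib was administered in combination with itraconazole, a strong CYP3A inhibitor". Fluconazole is moderate: simulations suggested that "a moderate CYP3A inhibitor (fluconazole) may increase the AUC and Cmax of olaparib by 2- and 1.1-fold". The section then refers the reader to Appendix B.

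Appendix B contains "TABLE 8: Drugs Known to be Inhibitors and inducers of CYP3A", with a column headed "Potent CYP3A inhibitors". Fluconazole and itraconazole are both in that column. The table has no moderate column, its introduction concerns AZD6738, and its management line is to stop or not use the listed drugs.

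The olaparib paragraph that closes Appendix B covers short-term use that cannot be avoided. It names no drug in either class:

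- Strong: "If a strong CYP3A inhibitor must be used, olaparib should be dose reduced to 100 mg daily for the duration of concomitant therapy". The reduced dose is then kept until 5 half-lives after the inhibitor stops.
- Moderate: "If a moderate CYP3A inhibitor must be used, olaparib should be reduced to 150 mg po twice a day". Here the reduced dose is kept until 3 half-lives after the inhibitor stops.

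Section 4.3.2 uses the same two classes for olaparib, which "may require dose reduction if a strong or moderate CYP3A is required for a short period while on study". For AZD6738 it speaks of a potent CYP3A inhibitor and requires interruption plus a five half-life washout.

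**The concern.** The olaparib dose during an unavoidable inhibitor depends only on the class of that inhibitor, and the protocol gives fluconazole two labels. Section 6.1 sends the reader to Appendix B, where the only CYP3A inhibitor list calls fluconazole potent. A site that stops at that label and treats potent as strong applies the 100 mg daily rule. A site that keeps the 6.1 label applies the 150 mg twice-daily rule.

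The same co-medication could therefore be handled with different olaparib doses and different times at the reduced dose. What is at stake is consistent dosing across the four centers and avoidable under-dosing of a patient during an antifungal course.

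**Working it through.** **Does potent mean strong?** The protocol does not define it so. Two places support the inference. Itraconazole is strong in 6.1 and is in the potent column of Table 8. Exclusion criterion 11 pairs potent with moderate for inhibitors, and strong with moderate for inducers, so each word names the class above moderate. Section 4.3.2 adds little, because its olaparib sentence omits the word inhibitor.

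**Daily dose.** Usual: 2 x 300 = 600 mg. Moderate rule: 2 x 150 = 300 mg, or 50% of usual. Strong rule: 100 mg, or 17% of usual. The two rules differ by 300/100 = 3-fold.

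**Exposure.** Inputs from 6.1 are the 2-fold AUC for fluconazole (simulated) and the 2.7-fold AUC for itraconazole (interaction trial). Section 6.1 also says that AUC rises less than proportionally over 100 to 400 mg, without giving a slope. I assume AUC proportional to dose^b, with b from 1.0 (proportional) to 0.7. Relative daily AUC = fold x (doses per day) x dose^b / (2 x 300^b).

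| Case | Formula | b = 1.0 | b = 0.7 |
|---|---|---|---|
| Fluconazole, moderate rule | 2 x 0.5^b | 1.00 | 1.23 |
| Fluconazole, strong rule | (1/3)^b | 0.33 | 0.46 |
| Itraconazole, strong rule | 1.35 x (1/3)^b | 0.45 | 0.63 |
| Level -2 (200 mg BID, Table 2), no inhibitor | (2/3)^b | 0.67 | 0.75 |

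The moderate rule fits the 6.1 figure: at b = 1, half the dose times a 2-fold AUC restores usual exposure. The strong rule applied to fluconazole gives 0.50 (b = 1) to 0.62 (b = 0.7) of level -2 exposure.

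**Loss over a 28-day cycle under the strong rule, before washout.** For an assumed course of L days, loss = L x (1 - relative AUC)/28.

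- L = 7: 7 x 0.667/28 = 17% at b = 1; 7 x 0.537/28 = 13% at b = 0.7.
- L = 14: 33% and 27%.

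**Extra time at the reduced dose.** 5 - 3 = 2 half-lives. The documents do not say whose half-life is meant and give none for fluconazole. An assumed 12 to 48 hours adds 2 x 12 h = 1 day to 2 x 48 h = 4 days.

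**The case against.** The best defence is that the olaparib text is consistent by itself. Section 6.1 and the Appendix B olaparib paragraph use the same two words, strong and moderate. Section 6.1 is the only place that classes fluconazole for olaparib, and together they give one answer: 150 mg twice a day. Reaching 100 mg daily means passing over that statement, borrowing a label from a list written for AZD6738, and inferring that potent equals strong. This stands. A reader might infer that the two doses are equally authorised by the text; the documents do not support that, because the 100 mg route needs an unstated equivalence.

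The situation is also narrow. Table 8 says to stop or not use the drug. Section 4.3.2 tells patients to avoid CYP3A modulators from screening until 28 days after the last dose. Exclusion criterion 12 gives a need for systemic antifungals as an example of what keeps a patient out at entry. This also stands. It leaves fluconazole that becomes unavoidable on study, which is the case the olaparib paragraph was written for.

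Finally, the protocol tolerates comparable short-term loss of exposure: 0.45 to 0.63 times usual with itraconazole under its own rule, and interruptions of up to 28 days for toxicity (5.4.1). That limits the importance of the conflict but does not remove it.

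**Conclusion.** The two labels conflict in the current text, and the cross-reference from 6.1 leads to the list with the other label. The better reading is 150 mg twice a day. The risk is that a site takes the Table 8 label and gives 100 mg daily with 5 half-lives of washout: a 3-fold lower daily dose and about 0.33 to 0.46 times usual exposure, against 1.0 to 1.23. These figures rest on the simulated 2-fold AUC and on the assumed range for b.

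Three stronger readings are not supported:

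- That exposure falls to one third of usual, or to half of the lowest planned level, without qualification. Both hold only at b = 1, and 6.1 says AUC is less than dose-proportional.
- That AZD6738 handling is also in doubt. Section 4.3.2 relies on the Appendix B lists and Table 8 includes fluconazole, so AZD6738 is interrupted.
- That the trial's inference is affected. The error is temporary under-dosing when fluconazole is unavoidable, with no frequency given in the documents. Eligibility is untouched (criterion 11 sets the same 2-week washout for both classes of inhibitor), as are the endpoint, type I error and power.

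This is a minor dosing-consistency point, worth correcting at the next amendment.

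**What to change.** Keep fluconazole in Table 8 for AZD6738. Add to the olaparib paragraph of Appendix B:

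*For olaparib dosing, fluconazole is a moderate CYP3A inhibitor (Section 6.1): reduce to 150 mg twice a day for the duration of fluconazole and for 3 half-lives afterwards. AZD6738 is still interrupted as in 4.3.2. The potent label in Table 8 governs AZD6738; apart from fluconazole, the potent inhibitors in Table 8 are treated as strong for olaparib.*

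The last sentence settles how the potent label carries over to olaparib. It does not class inhibitors that are absent from Table 8, such as ciprofloxacin and diltiazem, which criterion 11 gives as examples of potent or moderate inhibitors; sites must still class those from other sources.

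The cost is one short addition, with no change to the Table 8 entries, the AZD6738 rule, sample size, visits or analysis. The downside is that the 2-fold figure is simulated. If the true effect were as large as that of itraconazole, 150 mg twice a day would give 2.7 x 0.5^b = 1.35 (b = 1) to 1.66 (b = 0.7) times usual olaparib AUC for the course.
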